7.3. Statistical analysis for dose proportionality

7.3.1. Endpoints/Variables

Dose proportionality will be assessed following single doses of GSK3494245 separately for the fasted and fed cohorts during the Single Ascending Dose (SAD) via analyses of AUC (0-∞) and C_{max}. Only if required, the power model is fitted to dose normalized parameters to assess the dose proportionality for AUC (0-∞) and C_{max} (AUC(0-∞)_D and C_{max}_D).

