7.3.2. Main analytical approach

Power model will also be fitted to assess dose proportionality as follows: $y = \alpha * \text{dose}^\beta$. In the log transformed manner this power model can be written as following

$$\log_e(Y) = \beta \times \log_e(\text{dose}) + \log_e(\alpha)$$

Where, y denotes the PK parameter being analyzed, dose denotes the dose administered to a subject. α depends upon random intercept subject effect and period effect and β is the coefficient of covariate $\log(\text{dose})$.

Log_e transformed data will be analyzed using a mixed effect model:

- Fixed effect: loge (dose), period
 - Random effect: Subject
- Data from all available doses will be considered. An unstructured covariance structure will be considered for the G matrix describing the between subject variability. If this model fails to converge, alternative covariance structures may be considered such as Variance Component, Compound Symmetry, etc. Akaike's Information Criteria (AIC) will be used to assist with the selection of covariance structure.
 - The Kenward and Roger method for approximating the denominator degrees of freedom and correcting for bias in the estimated variance-covariance of the fixed effects will be used.
 - Distributional assumptions underlying the model used for analysis will be examined by obtaining a normal probability plot of the residuals and a plot of the residuals versus the fitted values (i.e., checking the normality assumption and constant variance assumption of the model respectively) to gain confidence that the model assumptions are reasonable.
 - If there are any departures from the distributional assumptions, alternative transformations, such as data squared or square root of data, will be explored.

Model Results:

- The estimates mean slopes and 90% CIs of $\log_e(\text{dose})$ will be presented. Note that a slope ≈ 1 implies dose proportionality.

If the power model is failed to converge, analysis will be performed using Analysis of Variance (ANOVA) model to assess dose proportionality. The PK parameters (AUC (0- ∞), Cmax) will be dose-normalized first and multiplying by reference dose prior to loge-transformation, will be analyzed separately using mixed effects model.

- Fixed effect: loge (dose), period
- Random effect: Subject

The reference dose will be chosen based on the lowest clinically relevant dose over which PK can be adequately described.

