- Data from all available doses will be considered. An unstructured covariance structure will be considered for the G matrix describing the between subject variability. If this model fails to converge, alternative covariance structures may be considered such as Variance Component, Compound Symmetry, etc. Akaike's Information Criteria (AIC) will be used to assist with the selection of covariance structure.
- The Kenward and Roger method for approximating the denominator degrees of freedom and correcting for bias in the estimated variance-covariance of the fixed effects will be used.

- Distributional assumptions underlying the model used for analysis will be examined by obtaining a normal probability plot of the residuals and a plot of the residuals versus the fitted values (i.e., checking the normality assumption and constant variance assumption of the model respectively) to gain confidence that the model assumptions are reasonable.
- If there are any departures from the distributional assumptions, alternative transformations, such as data squared or square root of data, will be explored.

Model Results:

Adjusted geometric means for each dose will be presented along with the standard errors (SE) and 90% CIs. Estimated treatment ratios to reference dose (First or lowest dose of each part) and corresponding 90% CI will also be presented.

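### The SAP 7.3.2 ANOVA fallback is the power model reparameterised: no real remedy for non-convergence and no free dose-level estimates; the dose-normalised option in 7.3.1 lacks its slope-0 benchmark

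*SAP*

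**What the plan says.** SAP 7.3.2 fits the loge-transformed PK parameter with "Fixed effect: loge (dose), period" and a random subject effect. The intercept "depends upon random intercept subject effect and period effect", so the random part is an intercept only. The result is the slope of loge(dose) with a 90% CI, and a slope near 1 is read as proportional.

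The contingency follows: "If the power model is failed to converge, analysis will be performed using Analysis of Variance (ANOVA) model to assess dose proportionality". For this model AUC(0-∞) and Cmax will be "dose-normalized first and multiplying by reference dose prior to loge-transformation, will be analyzed separately using mixed effects model". The fixed-effect and random-effect lines under it repeat those of the power model, and so do the covariance and Kenward-Roger provisions. Its results differ: "Adjusted geometric means for each dose will be presented along with the standard errors (SE) and 90% CIs", together with "Estimated treatment ratios to reference dose (First or lowest dose of each part"), again with 90% CIs. No slope and no slope benchmark are stated for the fallback.

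The reference dose is described a second time, just before these results: "The reference dose will be chosen based on the lowest clinically relevant dose over which PK can be adequately described".

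SAP 7.3.1 adds that, only if required, "the power model is fitted to dose normalized parameters to assess the dose proportionality", naming AUC(0-∞)_D and Cmax_D. It gives no separate reading of the slope for that use.

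Protocol 9.5.2 names only the power model. SAP 7.7 sends the MAD dose-proportionality analysis to 7.3.2, so the fallback applies there too.

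**The concern.** A fallback should either be easier to fit than the model it replaces or answer the question in another way. This one changes the response by a quantity that is already in the model, so it poses the same fitting problem. Its promised output looks like dose-by-dose ANOVA evidence, but with dose as a single continuous term it can only restate the fitted line. It could not show where along the dose range proportionality breaks down, which is what per-dose means and ratios are for.

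The option in 7.3.1 carries a related trap. The only slope reading in the section is about 1. Applied to dose-normalised data, that reading would call proportional pharmacokinetics non-proportional, and a slope of 1 would mean exposure rising with the square of dose.

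**Working it through.** **Inputs.** Model terms and outputs: SAP 7.3.1 and 7.3.2. Exposure figures for illustration: Protocol Table 6 means at 30, 60, 120, 180 and 240 mg (AUC 1819, 3828, 8057, 12450, 16955; Cmax 464.1, 862.4, 1603, 2303, 2978). Simulation: two cohorts of 8, four periods, 6 active and 2 placebo per period (Protocol 4.1.1); between-subject CV 30%, log SD 0.294 (SAP 8); within-subject log SD 0.198 (CV 20%, the SAP 8 value for AUC). Assumed: eight doses from 20 to 500 mg, a true slope of 1.1, and one dose level per period in each cohort. The last is inferred from the text, because the design figure is not shown.

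**1. Algebra.** Power model: log Y = a + β·log(D) + period + subject + error. Fallback response: log(Y × ref/D) = log Y − log(D) + log(ref). Substituting gives

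log(Y × ref/D) = (a + log ref) + (β − 1)·log(D) + period + subject + error.

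The design matrix is unchanged, so the residuals, REML objective and variance estimates are unchanged. Only the slope and intercept are relabelled.

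**2. Slope on the documents' figures.** Least-squares slopes on the Table 6 means, raw then dose-normalised:
- AUC: 1.0735 and 0.0735
- Cmax: 0.8940 and −0.1060
- exactly proportional data: 1.000 and 0.000

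The SAP's benchmark of about 1 is therefore right for untransformed exposure. On dose-normalised data the value is 0.

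**3. Fitted mixed models.** In 300 simulated data sets (half with 30% between-subject CV, half with zero between-subject variance), wherever both fits converged:
- the slopes differed by 1 to within 6e-10
- the standard errors differed by at most 8e-10
- the REML log-likelihoods differed by at most 2.4e-8

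A direct profile of the REML objective on a further 300 data sets agreed to about 1e-13 and had the same optimum in 300 of 300.

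**4. Convergence flags (statsmodels).** From the second 300:

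| Between-subject variance | Both converge | Power model only fails | Fallback only fails | Both fail |
|---|---|---|---|---|
| CV 30% | 150 | 0 | 0 | 0 |
| Zero | 120 | 13 | 11 | 6 |

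All 24 discordant data sets had their optimum at the zero-variance boundary. The flag moved in both directions at about the same rate, which is rounding and not a better-posed model.

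**5. Per-dose output.** With loge(dose) continuous, the fitted ratio to reference is (D/ref)^(β − 1). In one simulated curved example (reference 20 mg, within-subject log SD reduced to 0.05, period omitted from both fits):

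| Dose | True ratio | Line | Dose as factor |
|---|---|---|---|
| 60 mg | 0.705 | 0.890 | 0.682 |
| 500 mg | 1.000 | 0.710 | 0.844 |

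The true ratios fall and then rise; the line can only fall. The factor estimates carry sampling error but follow the shape.

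**6. Dose as a factor together with period.** With eight dose levels there are 1 + 7 + 3 = 11 columns, and the rank is 8. If DL4 is repeated there are 1 + 6 + 3 = 10 columns, and the rank is again 8. Under the inferred layout, factor dose and period cannot both be estimated freely.

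**The case against.** The best defence is that this is a copying slip. The ANOVA label, the per-dose adjusted means and the ratios to a reference all point to dose as a factor, and a programmer might well code it so. The fallback would also rarely be reached: at the plan's 30% CV every simulated fit converged. The protocol names only the power model, and dose-normalised parameters are among those derived in SAP 7.1, so some descriptive view of proportionality exists anyway. All of this limits the importance of the point. It does not make the written model consistent with its own outputs. The prior step of trying other covariance structures adds little either, because with a random intercept alone there is a single between-subject variance to describe.

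Three stronger readings are tempting but not supported.
- A reader might infer that the fallback fails whenever the power model does. The estimation problem is the same, but a software flag can differ at a zero variance, as step 4 shows.
- A reader might infer that no per-dose means can be produced. A loge(dose) covariate does give a predicted mean, SE and CI at each dose, and a ratio; they are just not free estimates.
- A reader might infer that the fallback has the wrong benchmark. The slope of about 1 belongs to the power model's results, where it is correct, and the fallback reports ratios with no slope benchmark. The gap lies only in the dose-normalised power model of 7.3.1.

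The two reference-dose descriptions are a wording matter. The scaling constant cancels from slopes and ratios, so only the comparator for the ratios matters, and the two descriptions may coincide.

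**Conclusion.** The point holds as an error in the written contingency analysis for a secondary objective. As listed, the 7.3.2 fallback is the power model with its slope lowered by exactly 1. This follows from the algebra and does not depend on the simulated doses. It gives no real remedy for non-convergence, and its per-dose ratios are constrained to one line. The 7.3.1 option lacks the correct benchmark, slope 0, and the only reading on the page is off by 1 for that use.

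The practical reach is small. How often the fallback would be used cannot be derived from the documents, and the simulation suggests rarely at 30% CV. Nothing here changes the main power-model analysis of untransformed exposure. The size of the distortion in step 5 is illustrative only, and the rank result in step 6 rests on the inferred layout of one dose level per period within a cohort.

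**What to change.** In the SAP 7.3.2 fallback:
- Replace loge(dose) with dose level as a categorical fixed effect, keeping subject random.
- State that ratios to the reference dose near 1 indicate proportionality.
- Drop period from this fallback, or state how it is handled given its overlap with dose level.
- Give one definition of the reference dose used for the ratios.

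In SAP 7.3.1, either delete the power model on dose-normalised parameters, which adds nothing beyond the shifted slope, or state that slope 0 is its benchmark.

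The cost is a few lines of text and one changed model statement. The categorical model spends more degrees of freedom: under the simulated layout, 8 fixed-effect parameters against 5 for intercept, slope and period, with about 6 active records per dose (8 participants × 3 active doses ÷ 4 dose levels). Without a period term, any period effect is absorbed into the dose means, and the report should say so.

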7.3.2.1. Intercurrent events and handling of missing data

The intercurrent events mentioned in Section 1.1.2. along with the corresponding strategies will be considered during this analysis.

- For treatment discontinuation due to any reason:
Subjects' data available up to the withdrawal will be included in the analysis where treatment discontinuation had not occurred. If a subject withdraws consent during a period, the missing data post withdrawal will not be imputed.
- For Subject use concomitant/prohibited medication:
The subject data post consumption of concomitant/prohibited medications (intercurrent event) will be analyzed as collected.

If multiple intercurrent events are observed, then the data will be handled using more than one strategy as described in Section 1.1.2. and interpretations of the results will be made accordingly.

Graphical presentations will be provided, if appropriate. All data will be listed. Details of the planned displays are provided in the Output Programming Specification (OPS) document. Data Displays will be based on GSK Data Standards and statistical principles.

7.4. Statistical analysis for Accumulation

7.4.1. Endpoints/Variables

- The extent of accumulation of GSK3494245 will be based on AUC(RAUC_(0-tau)), C_{max} (RC_{max}) and C_{tau} (RC_{tau}).

7.4.2. Main analytical approach

Statistical analysis will be to estimate the accumulation ratio, R_o , on the pharmacokinetics of GSK3494245. Following \log_e -transformation, AUC(0-tau) on Day 1 and AUC(0-tau) on the day of last dose will be analyzed by a mixed effect model.

- Fixed effect: dose, day, and dose*day
- Random effect: Subject
- Data from all available doses will be considered. An unstructured covariance structure will be considered for the G matrix describing the between subject variability.
- The Kenward and Roger method for approximating the denominator degrees of freedom and correcting for bias in the estimated variance-covariance of the fixed effects will be used.
- Distributional assumptions underlying the model used for analysis will be examined by obtaining a normal probability plot of the residuals and a plot of the residuals versus the fitted values (i.e., checking the normality assumption and constant variance assumption of the model respectively) to gain confidence that the model assumptions are reasonable.
- If there are any departures from the distributional assumptions, alternative transformations such as data squared or square root of data, will be explored.
- If this model fails to converge, alternative covariance structures may be considered in the following order (1) Compound Symmetry (CS) and (2) Variance Components (VC) (3) First order autoregressive.

Model Results:

- For each dose, point estimates and 90% confidence intervals for the differences “Day 7 - Day 1” (for BID) or “Day 6 evening dose - Day 1 morning dose” (for TID) will be constructed using the appropriate error term.
- The geometric mean ratio and 90% CI for the ratios “Day 7: Day 1” (for BID) or “Day 6- Day 1” (for TID) after back transformation for each active dose.
- If both the dose and day by dose interaction terms are not significant, a single point estimate and confidence interval pooled across all doses will also be constructed.

Note: RCmax and RCtau will be estimated in a similar approach

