- The SAD part will consist of a single-dose escalation phase in up to 3 cohorts and a food effect cohort.
- Cohorts 1 and 2 will comprise of a 4-way crossover within each cohort. Participants will receive three doses of GSK3494245 and a randomised placebo dose, administered in the fasted state. An optional third cohort may be included to further evaluate safety or PK or to evaluate additional doses.
- Cohort 3 will investigate the effect of food following a single dose. It will comprise of a 4-way crossover in which participants will receive GSK3494245 and placebo in both fasted and fed conditions and in a 1:1 ratio.
- On completion of Cohort 3, Cohort 3a will assess single ascending doses of GSK3494245 taken with food, following the same 4-way crossover design as Cohorts 1 and 2. Participants will receive three doses of GSK3494245 and a randomised placebo dose. An optional cohort may be included to further evaluate safety or PK or to evaluate additional dose levels.
- Up to 8 10 different dose levels will be studied in the SAD part.
- The MAD part will be a twice-daily (BID) 7-day repeat dose design in up to 5 cohorts of participants (Cohorts 4, 5, 6, 7 and 8), with doses administered in the fed state. Based on emerging data, the dosing regimen may be altered to a three-times daily (TID) regimen in fed conditions, with the three doses administered 6 hours apart on each day.. Up to a maximum of 5 dose levels will be studied in the MAD part. CCI [REDACTED]
[REDACTED]

All participants in the study will attend a screening visit within 28 days prior to their first dose and a follow-up visit within 7-14 days after their final dose. If required, additional follow-up visits may be scheduled.

Disclosure Statement: This is a sequential, cross-over (SAD part, within cohort), parallel group (MAD part), interventional study that is participant, investigator and sponsor study team blinded (apart from unblinded team members, prespecified in the protocol).

Number of Participants:

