4. STUDY DESIGN

4.1. Overall Design

This study will be a randomised, double-blind, placebo-controlled, 2-part study of the oral administration of GSK3494245 in healthy participants. As this will be the first time GSK3494245 is administered to humans, the study design may change based on emerging data as the study progresses.

This study is planned to include approximately 80 participants and will consist of 2 parts:

- The SAD part will consist of a single-dose escalation phase in up to 3 cohorts and a food effect cohort.
- Initially, Cohorts 1 and 2 will comprise of a 4-way crossover within each cohort which includes 4 dosing regimens under fasted conditions. An optional third cohort may be included to further evaluate safety or PK or to evaluate additional dose levels.
- Cohort 3 will investigate the effect of food on the safety, tolerability and PK of a single dose. It will comprise of a 4-way crossover in which participants will receive GSK3494245 and placebo in both fasted and fed conditions and in a 1:1 ratio.
- On completion of Cohort 3, Cohort 3a will assess single ascending doses of GSK3494245 taken with food, following the same 4-way crossover design as Cohorts 1 and 2. An optional cohort may be included to further evaluate safety or PK or to evaluate additional dose levels.
- Up to a maximum of 10 different dose levels will be studied in the SAD part.
- The MAD part will be a twice-daily (BID) 7-day repeat dose design in up to 5 cohorts of participants (Cohorts 4, 5, 6, 7 and 8) although the dosing regimen may be altered to TID dosing depending on emerging data, with doses administered 6 hours apart on each day. Up to a maximum of 5 dose levels will be studied in the MAD part, with doses administered in the fed state. CCI

All participants in the study will attend a screening visit within 28 days prior to their first dose and a follow-up visit within 7-14 days after their final dose. If required, additional follow-up visits may be scheduled. Participants may only take part in one study cohort.

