4.4. Scientific Rationale for Study Design

This study will be the first administration of GSK3494245 in human participants. The primary purpose of the current study is to characterise the safety and tolerability of GSK3494245 in healthy participants within a controlled PK range. The study will additionally seek to understand the secondary and exploratory endpoints. Specific scientific considerations which contribute to the study design include:

- In the SAD part, this study employs a randomised sequential crossover design to allow for dose comparison between and within participants at different dose levels. In addition, this design minimises participant numbers across the SAD part of the study and is appropriate given the short-estimated half-life of GSK3494245 (approximately 4 h), which enables a short washout period.
- Furthermore, a food-effect evaluation is planned to support progression into patient studies. An assessment of food effect on the exposure to GSK3494245 will be incorporated into the SAD part of the study. Preliminary assessment of food-effect hinted a marginal decrease in the drug exposure which could possibly be attributed to high stomach solubility in the fasted acidic stomach that is not present in the fed state due to a higher pH. In the presence of food, the exposure may be slightly lower or the same in terms of overall trend. Please see Section 9 for further details on how sample size was determined for the food effect cohort. The exact sample size for the evaluation of the food effect will be determined based on the variability of the AUC and C_{\max} observed in Cohorts 1 and 2. Up to a maximum of 16 participants will be recruited to allow for 12 evaluable participants, however as few as 10 evaluable participants may be required, in which case the number of participants recruited could be slightly lower. The

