4.5. Justification for Dose

4.5.1. Human Predicted Pharmacokinetics

The preclinical pharmacokinetic (PK) data (mouse, rat and dog) was used to predict human blood PK parameters. Briefly, mouse, rat and dog in vitro and in vivo ADME datasets were employed to get the human PK estimates using various scaling approaches. The GlaxoSmithKline software package PK Predictor Pro (GUI v1.1.45 Calculation Engine v1.4.4) was used for IVIVE (in vitro-in vivo extrapolation), LBF (liver blood flow) and allometric scaling. GastroPlus 9.0 (Simulation Plus, inc.) was applied for the PBPK modelling [GlaxoSmithKline Document Number [2018N371507_02](#)]. NONMEM 7.4.3 (Icon Development Solutions) was used for PK simulations in human, based on GastroPlus parameters.

The different scaling methods predicted a clearance (CL) range of 3-11 mL/min/kg. Two clearance values were obtained based on the fact that the hepatocytes intrinsic clearance

in dog and human was shown to be saturated at increasing concentrations of the compound: a low clearance $CL=3.81$ mL/min/kg, and a high clearance $CL=6.67$ mL/min/kg. Both values were considered to predict human PK. The predicted steady state volume of distribution (VDSS) ranged from 0.7 to 2.2 L/kg with an average estimate of 1.28 L/kg, which was used to predict human PK. Taking into account only the liver extraction, human oral bioavailability is expected to be moderate (47 to 78%). Across the preclinical species (mouse, rat, beagle dog), a range of bioavailability values from 18 to 86% was observed. A value of 80% bioavailability was used for human PK prediction in the low clearance scenario, while a 64% bioavailability in the high clearance scenario [GlaxoSmithKline Document Number [2018N371507_02](#)].

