	
In the event the DEC decide there is a need to address any concerns from a safety or PK point of view, the 4th dose level (DL4) may be repeated at the start of Cohort 2. Thereby allowing up to 7 dose levels to be studied, in this scenario. In addition, the DEC may decide, based on emergent safety and PK data to include an additional cohort of up to 8 participants following the same design as Cohorts 1 and 2.
 
Food Effect:
 
Cohort 3 will consist of up to 16 healthy participants and will comprise of a 4-way crossover in which participants will receive GSK3494245 and placebo in both fasted and fed conditions. The selected dose level (DLX) to investigate the effect of food on the safety, tolerability, and PK of a single dose of GSK3494245 will be one already evaluated from a previous intervention period.
 
Cohort 3a will comprise of 4 intervention periods, investigating 4 dosing regimens under fed conditions. Participants will receive three doses of GSK3494245 and a randomised placebo dose, administered in the fed state.
 
Washout: At least 48 hrs. or 5-half-lives (whichever is longer) will be given between each dose for an individual participant.
 
Note: Participants will be admitted to the unit the day before dosing (Day -1) and will remain in the unit overnight until Day 4 of intervention.
 
MAD:
 
The MAD part will be a twice-daily (BID) or three-times daily (TID) 7-day repeat dose design in up to 5 cohorts (Cohorts 4, 5, 6, 7 and 8), each including 8 participants. Dependent on whether a food effect is observed in the SAD phase, the MAD part may also include drug administration after either fed or fasted conditions. Up to a maximum of 5 dose levels will be studied in the MAD part. CCI
 
Note: Participants will be admitted to the unit the day before dosing (Day -1) and will remain in the unit overnight until Day 8.

Dosing	
Dose Escalation (SAD):
 
 For Cohorts 1 and 2, each participant will receive a maximum of 3 ascending oral doses of GSK3494245 and 1 placebo dose under fasted conditions (4 regimens) in a crossover manner.

Overview of Study Design and Key Features	

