7.6.2. Main analytical approach

A statistical analysis will be performed using mixed effect model on log_e transformed endpoint.

- Fixed effect: log(dose)
- Random effect: Subject
- Data from all available doses will be considered. An unstructured covariance structure will be considered for the G matrix describing the between subject variability.
- The Kenward and Roger method for approximating the denominator degrees of freedom and correcting for bias in the estimated variance-covariance of the fixed effects will be used.
- Distributional assumptions underlying the model used for analysis will be examined by obtaining a normal probability plot of the residuals and a plot of the residuals versus the fitted values (i.e., checking the normality assumption and constant variance assumption of the model respectively) to gain confidence that the model assumptions are reasonable.
- If there are any departures from the distributional assumptions, alternative transformations such as data squared or square root of data, will be explored.
- If this model fails to converge, alternative covariance structures may be considered in the following order (1) Compound Symmetry (CS) and (2) Variance Components (VC) (3) First order autoregressive.

Model Results:

- The coefficients of the slopes for the day effect on log scale for each dose, along with corresponding 90% confidence intervals, will be used to determine whether steady state was achieved.

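### If both BID and TID cohorts are run, the SAP's repeat-dose models have no regimen term, and the single dose-proportionality slope in SAP 7.7 would confound regimen with dose

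*SAP*

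**What the plan says.** Protocol 1.1 plans BID dosing in the MAD part and adds that "the dosing regimen may be altered to a three-times daily (TID) regimen in fed conditions". Protocol 4.1 and 4.1.4 repeat the option. Neither document says that all of Cohorts 4 to 8 must use one regimen.

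The SAP's MAD models are:

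- **7.4.2, accumulation:** "Fixed effect: dose, day, and dose*day", with subject random. The contrast is Day 7 against Day 1 for BID and Day 6 evening against Day 1 morning for TID, reported by dose. An additional pooled estimate is given if the dose and interaction terms are both non-significant.
- **7.5, time invariance:** day only.
- **7.6.2, steady state:** the listed term is "Fixed effect: log(dose" (closing bracket omitted here). There is no day term, although day slopes by dose are promised.
- **7.7, MAD dose proportionality:** the power model of 7.3.2 (log dose and period), applied to Day 1 and to Day 7 (BID) or Day 6 (TID).

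The models in 7.3.2, 7.4.2, 7.5 and 7.6.2 all take in every available dose. None contains regimen. The SAP does not say whether dose in the MAD models means mg per administration, daily total or cohort, nor whether Day 6 evening and Day 7 are one level of day.

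On food, SAP 1.2 says that "the MAD part may also include drug administration after either fed or fasted conditions", while Protocol 4.1 describes the MAD part "with doses administered in the fed state".

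**The concern.** The two regimens do not yield like quantities. The interval is 12 h against 6 h, and the last profile follows a different dose history: for TID it is the third dose of Day 6, taken 6 h after the second. More drug is carried over under TID, so the last-dose Cmax per mg is higher even when PK is exactly linear.

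Dose escalates from cohort to cohort. If the switch comes during escalation, TID falls on the higher doses. A single log-dose slope then attributes the carry-over to dose, and proportional PK looks supra-proportional. In the accumulation model the corresponding risk is one ratio that averages two different true values and describes neither regimen.

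**Working it through.** **Inputs.** Protocol 4.5.1 gives "a low clearance $CL=3.81$ mL/min/kg, and a high clearance $CL=6.67$ mL/min/kg", a volume "with an average estimate of 1.28 L/kg, which was used to predict human PK", and an absorption rate constant of 0.7 per h. SAP 1.2 gives the dosing intervals, a single dose on Day 7, and 6 active participants per cohort.

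**Reproducing the plan's figures.** k = CL × 0.06 / V, so 3.81 × 0.06 / 1.28 = 0.179 per h and 6.67 × 0.06 / 1.28 = 0.313 per h. Half-life = ln 2 / k = 3.88 h and 2.22 h. The first matches Protocol 4.4, which calls the crossover "appropriate given the short-estimated half-life of GSK3494245 (approximately 4 h), which enables a short washout period". The stated precision also reproduces: exp(2.571 × 0.294 / √6) − 1 = 36%.

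**Accumulation by superposition.** One compartment, linear PK, unit-dose curve proportional to exp(−kt) − exp(−ka·t), summed over all doses. BID compares the 12 h after the Day 7 dose with the first 12 h. TID (0, 6 and 12 h each day) compares the 6 h after the Day 6 evening dose with the first 6 h.

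| Half-life, ka | RAUC BID / TID | RCmax BID / TID | RCtau BID / TID |
|---|---|---|---|
| 3.88 h, 0.7 per h | 1.19 / 1.77 | 1.18 / 1.68 | 1.13 / 1.50 |
| 2.22 h, 0.7 per h | 1.04 / 1.35 | 1.04 / 1.33 | 1.02 / 1.19 |
| 2 h, 3 per h (assumed) | 1.02 / 1.16 | 1.02 / 1.16 | 1.02 / 1.14 |
| 1.5 h, 3 per h (assumed) | 1.00 / 1.08 | 1.00 / 1.08 | 1.00 / 1.07 |

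Keeping ka at 0.7 with the shorter half-lives gives TID RAUC of 1.18 (1.5 h) and 1.30 (2 h). Across both absorption assumptions, TID RAUC at 1.5 to 2 h is therefore about 1.1 to 1.3.

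**SAP 7.7 slope.** Assumed allocation: 30, 60 and 120 mg BID, then 180 and 240 mg TID (the mg values of Table 6), equal cohorts, dose coded as mg per administration.

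- Log doses are 3.401, 4.094, 4.787, 5.193 and 5.481, with mean 4.591 and Sxx = 2.855.
- The two TID cohorts contribute 0.602 + 0.889 = 1.491, so the weight is 1.491 / 2.855 = 0.522.
- Expected slope = 1 + 0.522 × ln(RCmax TID / RCmax BID).
- Low clearance: 1 + 0.522 × ln(1.684 / 1.182) = 1.18. High clearance: 1 + 0.522 × ln(1.327 / 1.044) = 1.13.
- Half-life 2 h, ka 3: 1 + 0.522 × ln(1.16 / 1.02) = 1.07. Half-life 1.5 h, ka 3: 1 + 0.522 × ln(1.08 / 1.00) = 1.04. With ka 0.7 these become 1.11 and 1.08.

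Day 1 slopes are not shifted, because no earlier dose is on board. A slope on last-dose AUC(0-tau) would hardly move: 1 + 0.522 × ln(0.96) = 0.98 at worst. The illustration therefore concerns Cmax.

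**Against the precision of the slope.** With 30 active participants and an assumed log-scale SD of 0.294, SE = 0.294 / √(6 × 2.855) = 0.071, and the 90% half-width is 1.701 × 0.071 = 0.12. The Table 3 shifts are as large as that; the shorter half-life shifts with fast absorption are not.

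**SAP 7.4.2.** At different mg doses, the dose-by-day term gives each cohort its own ratio. At the same mg dose, coded as mg, equal cohorts would average to √(1.187 × 1.768) = 1.45 or √(1.044 × 1.353) = 1.19.

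**Pooling rule.** In 20,000 simulated trials per setting (6 per cohort, between-participant CV 30%, tests at an assumed 0.05), the dose term was never non-significant over five Table 6 doses, so pooling did not occur. With only 180 mg and 240 mg, one BID and one TID, and true ratios of 1.15 and 1.6, the rule allowed pooling in 10%, 21% and 35% of trials at within-subject CV 15%, 20% and 30%.

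**Time invariance.** The expected ratio is 1.00 for BID and 0.96 to 0.99 for TID.

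**The case against.** The strongest reply is that this is conditional. TID is described as an alternative regimen, and the documents never say that both will be run. There are five cohorts and at most five dose levels, so cohort and dose level may coincide. The SAP also labels its accumulation contrasts by regimen. All of this stands, and it limits the point.

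A reader might infer that BID and TID accumulation ratios will be merged or pooled as a matter of course. The documents do not support that. Merging needs both regimens at the same mg dose, dose coded as mg, and the last-dose day treated as one level. Pooling needs a non-significant dose effect on values that are not dose-normalised, which is practically out of reach over the Table 6 range.

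A reader might also infer that a merged ratio would decide the regimen. The SAP describes analyses for the study report; Protocol 4.6.3 leaves progression and the starting dose (BID or TID) to the dose escalation committee on accumulating data.

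The size is open to challenge too. Table 3 is preclinical. In Table 6, which rests on SAD data, AUC(0-12)/Cmax runs from 1819 / 2 / 464.1 = 2.0 h to 16955 / 2 / 2978 = 2.8 h. On a one-compartment reading this points to a half-life of no more than about ln 2 × 2.0 = 1.4 h to ln 2 × 2.8 = 2.0 h. The smaller figures may therefore be nearer the truth, although a profile with more than one phase could keep a longer tail.

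What the reply does not remove is SAP 7.7. There the confounding needs no shared mg dose, only a switch during escalation, which the protocol permits.

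**Conclusion.** The point holds conditionally. If both regimens are run, SAP 7.7 as written would bias the last-dose Cmax slope upward: to about 1.13 to 1.18 with Table 3 inputs, or about 1.04 to 1.07 at an assumed half-life of 1.5 to 2 h with fast absorption (1.08 to 1.11 with the protocol's absorption constant). These figures assume linear one-compartment PK and a switch to TID at the two highest doses. A different switch point changes the weight; if the switch comes during ascending-dose escalation, the direction stays the same.

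In SAP 7.4.2 merging is possible only under the narrower conditions above. RAUC would then combine 1.04 to 1.19 (BID) with 1.35 to 1.77 (TID) under Table 3, or about 1.0 with about 1.1 to 1.3 at the shorter half-life. The pooled estimate is a minor risk, and time invariance is barely touched under linear PK.

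The fed-or-fasted sentence is an unconditional but separate inconsistency of wording.

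**What to change.** In SAP 7.4.2, 7.5, 7.6.2 and 7.7, state that BID and TID cohorts are fitted in separate models and that no estimate is pooled across regimens. In 7.4.2, coding dose as dose × regimen is an acceptable alternative. That recoding does not carry over to 7.5, which has no dose term, or to 7.7, where it would remove the slope being estimated. State also how dose and day are coded. Separate fitting does not supply the day term missing from 7.6.2, which needs its own correction.

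Separately, reconcile the fed-or-fasted sentence in SAP 1.2 with the fed-only MAD text in Protocol 4.1 and 4.1.4. If the protocol text stands, the models need no food term.

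The cost is SAP wording, plus precision if both regimens are run. In the allocation assumed above, the split is 18 BID and 12 TID participants instead of 30 together. With TID at 180 and 240 mg only, Sxx = 0.288² / 2 = 0.041, so SE = 0.294 / √(6 × 0.041) = 0.59. The 90% half-width is then 1.812 × 0.59, about 1.07, so a TID slope from two close doses would say very little and the report should present it as descriptive.
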